11.1.3 Clinical laboratory evaluations

Hematology, coagulation, serum chemistry, serum pregnancy, urinalysis, immunology, immunophenotyping, and all other laboratory parameters including those listed in [Protocol Section 5.6](#) will be analyzed at multiple laboratory sites and will be delivered via hard-copy reports to the central data processing center (VSI). Laboratory test names and units of measurement will be standardized by VSI. For select parameters, study day, collection lab, date and time collected, normal range, observed value, change from baseline in relationship to both first and most recent implant, out-of-range flag, and Common Terminology Criteria for Adverse Events (CTCAE) v3.0 toxicity grade (if applicable) will be listed. Laboratory observations with Grade 3 or higher toxicity and/or reported as an AE will be listed. For all parameters, study day, date collected, observed value, normal range, and out-of-range flag will be output to a spreadsheet. For select parameters, observed values and changes from baseline (in relationship to both first and most recent implant) will be summarized for each time point at which laboratory data were collected. Separate series of tables will show numbers and percentages of subjects by out-of-range flag and by toxicity grade. Shift tables will be provided that show numbers and percentages of subjects with normal ↔ abnormal shifts based on out-of-range flags and/or toxicity grades from baseline (in relationship to both first and most recent implant) to each subsequent time point at which laboratory data are collected.

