4.3 Selection of Study Population

4.3.1 Inclusion Criteria:

1. Histologically-confirmed adenocarcinoma of the pancreas, colon, or rectum.
2. Radiographic evidence of metastatic cancer of the colon or rectum
3. The subject has pancreatic cancer that is unresectable or already metastatic or colorectal cancer that has failed available treatment modalities.
4. For the pancreas subjects, he/she may be accepted without prior chemotherapy or with multiple therapies that have failed. The colon and rectal cancer subjects must have failed available chemotherapy/targeted regimens. There is no limit to the number of prior chemotherapeutic regimens.
5. The subject must have evidence of progressive disease defined as at least one of the following:
 - a. Progressive measurable disease: using conventional solid tumor criteria
 - b. Increasing tumor markers and/or activity on PET-CT SUV measurement
6. All clinically significant toxic effects (excluding alopecia) of prior surgery, radiotherapy, or hormonal therapy have resolved to \leq Grade 1 based on the NCI-CTCAE v 3.0, with the exception of peripheral neuropathy, which must have resolved to Grade \leq 2.
7. The subject has an Eastern Cooperative Oncology Group performance status (ECOG PS) of 0-2.
8. The subject has adequate hematologic function (minimum requirements: absolute neutrophil count [ANC] \geq 1500/mL, hemoglobin \geq 9 g/dL, and platelets \geq 100,000/mL).
9. The subject has adequate hepatic function (bilirubin \leq 1.5 times the upper limit of normal (ULN)), aspartate transaminase [AST] and alanine transaminase [ALT] \leq 3 times the ULN, or \leq 5 times the ULN, if liver metastases are present).
10. The subject has adequate renal function (creatinine \leq 2.0 mg/dL)
11. The subject has adequate coagulation function (an international normalized ratio [INR] \leq 1.5 and a partial thromboplastin time [PTT] \leq 5 seconds above the ULN [unless on oral anticoagulant therapy]). Subjects receiving full-dose anticoagulation therapy are eligible provided they meet all other criteria, are on a stable dose of oral anticoagulant or low molecular weight heparin (and if on warfarin have a therapeutic INR between 2 and 3).
12. The subject has a life expectancy of 6 weeks.
13. The subject is male or female and at least 18 years of age. For females of childbearing potential, a negative pregnancy test is required.
14. The subject agrees to use contraceptives (barrier method) while on study, if sexually active.

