15. The subject has provided signed informed consent.

4.3.2 Exclusion Criteria:

1. Any condition (cardiovascular or other), making subject an unacceptably high anesthetic or surgical risk based on current anesthesia/general surgery standards.
2. Positive testing for HIV.
3. Cognitive impairment sufficient to render the subject incapable of giving informed consent.
4. Hypersensitivity reaction that, in the opinion of the investigators, poses an increased risk of an allergy to the macrobeads, particularly any known allergy to murine antigens or body tissues.
5. Surgical treatment or chemotherapy within three weeks of scheduled macrobead implantation or within four weeks of bevacizumab (or similar drugs), or radiation therapy within four weeks of scheduled macrobead implantation.
6. Investigational medications for their respective tumors within one month of baseline evaluation.
7. The subject has inadequate hematologic function (absolute neutrophil count [ANC] <1500/mL, hemoglobin <9 g/dL, and platelets <100,000/mL).
8. The subject has inadequate hepatic function [bilirubin >1.5 times the upper limit of normal (ULN)], aspartate transaminase [AST] and alanine transaminase [ALT] > 3 times the ULN, or > 5 times the ULN, if liver metastases are present).
9. The subject has inadequate renal function (serum creatinine > 2.0 mg/dL).
10. The subject has inadequate coagulation function (an international normalized ratio [INR] > 1.5 and a partial thromboplastin time [PTT] > 5 seconds above the ULN [unless on oral anticoagulant therapy]). Subjects receiving full-dose anticoagulation therapy are eligible provided they meet all other criteria, are on a stable dose of oral anticoagulant or low molecular weight heparin (and if on warfarin have a therapeutic INR between 2 and 3).
11. Hepatic blood flow abnormalities: portal vein hypertension and thrombosis; and/or large volume of ascites.
12. Concurrent cancer of any other type except skin cancer (excluding melanoma).
13. History of allergic reactions to mouse antigen.
14. The subject has an ongoing or active infection, symptomatic congestive heart failure, unstable angina pectoris, serious cardiac arrhythmias, (well-controlled atrial fibrillation, is permitted,) psychiatric illness/social situations that could interfere with the subject's ability to participate in the protocol, active bleeding.

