16.2 Tables

Table #	Tables
14.1.1.1	Completion / withdrawal
14.1.1.2.1	Subject disposition, 1 implant
14.1.1.2.2	Subject disposition, 2 implants
14.1.1.2.3	Subject disposition, 3 implants
14.1.1.2.4	Subject disposition, 4 implants
14.1.2.1	Baseline characteristics
14.1.2.2	Contraception methods
14.1.2.3.1	Presenting oncology diagnosis
14.1.2.3.2	Previous oncology diagnosis
14.1.3	Con meds by drug class and preferred name
14.1.4	Number of Implantations and number of macrobeads implanted
14.2.1.1	Global Clinical Assessment
14.2.1.2	Activities of Daily Living
14.2.1.3	Quality of Life Scale (imputed)
14.2.1.3X	Quality of Life Scale (not imputed)
14.2.1.4.1	Pain Scale Assessment, Pain Level
14.2.1.4.2	Pain Location
14.2.1.5	ECOG
14.2.2.1	Tumor markers
14.2.2.2	Cytokines
14.2.3	Tumor size and state
14.2.4	Overall survival (from the most recent radiological scan showing evident disease progression to death)
14.2.5	Time from first implantation to death
14.2.6	Time from diagnosis of Stage IV disease to death
14.3.1.1.1	AE summary
14.3.1.1.2	Death summary
14.3.1.2	Treatment-emergent AEs by SOC
14.3.1.3.1	Treatment-emergent AEs by SOC and preferred term
14.3.1.3.2	Treatment-emergent AEs by severity
14.3.1.3.3	Treatment-emergent AEs by relationship
14.3.1.6	Treatment-emergent frequently reported ($\geq 2\%$ in all patients combined) AEs
14.3.2	Treatment-emergent SAEs by severity
14.3.4.1.1	Serum Chemistry Observed & Changes

Table #	Tables
14.3.4.1.2	Serum Chemistry, out of range flags
14.3.4.1.3	Serum Chemistry, Shift Table
14.3.4.1.4	Serum Chemistry Toxicity Grades
14.3.4.2.1	Hematology Observed & Changes
14.3.4.2.2	Hematology, out of range flag
14.3.4.2.3	Hematology, Shift Table
14.3.4.2.4	Hematology Toxicity Grades
14.3.5.1	Physical exam
14.3.6.1	Vital signs
14.3.6.2	Vital signs from diary
14.3.7	ECG

Mortality Figures	
16.2.6.4.1	Overall survival (from the most recent radiological scan showing progression)
16.2.6.5.1.1	Time from first implantation to death
16.2.6.5.1.2	Time from diagnosis of Stage IV disease to death

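### The physical-examination table reports prevalence although the stated outcome is change from baseline; a smaller, related gap lies in the laboratory shift tables

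*SAP*

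**What the plan says.** **Examination.** SAP 3.3.2 lists change from baseline in physical-examination parameters among the safety outcomes and places weight, vital signs and ECG under that heading. SAP 11.1.6 then records each body system as normal, abnormal or not examined, lists this per subject, and summarises how many subjects, and what percentage, are abnormal in each system. The matching output is Table 14.3.5.1. No comparison with the subject's own baseline status is described for the table. Clinically significant changes that meet the adverse-event definition go to the AE form.

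**Laboratory.** SAP 11.1.3 plans shift tables of "normal ↔ abnormal shifts based on out-of-range flags and/or toxicity grades from baseline (in relationship to both first and most recent implant"). They appear in SAP 16.2 by title only: "Serum Chemistry, Shift Table" (14.3.4.1.3) and "Hematology, Shift Table" (14.3.4.2.3). The same section also says: "Separate series of tables will show numbers and percentages of subjects by out-of-range flag and by toxicity grade". For high grades: "Laboratory observations with Grade 3 or higher toxicity and/or reported as an AE will be listed".

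**Eligibility.** Protocol 4.3.2 item 8 excludes subjects with "bilirubin >1.5 times the upper limit of normal" or with "aspartate transaminase [AST] and alanine transaminase [ALT] > 3 times the ULN, or > 5 times the ULN, if liver metastases are present", so lower but still abnormal values are admitted. Protocol 4.3.1 item 6 begins "All clinically significant toxic effects (excluding alopecia) of prior surgery, radiotherapy, or hormonal therapy have resolved to" and sets the limit at Grade 1, or Grade 2 for peripheral neuropathy.

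**The concern.** The trial has no control arm, and the protocol treats each subject as his or her own reference. For safety data of this kind, the informative quantity is how many subjects became abnormal, or more abnormal, after implantation. The eligibility criteria make abnormal baselines foreseeable: raised transaminases or bilirubin in the laboratory data, and residual neuropathy or other treatment effects at examination.

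A table of abnormal findings at a visit mixes conditions present at entry with those that appeared later. The stated examination outcome is therefore not what the planned summary reports. The laboratory shift tables have a related but smaller weakness. A subject who is abnormal before implantation and worse afterwards is abnormal both times, so a normal/abnormal shift table records no shift.

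**Working it through.** The plan gives no figure on this point to reproduce. The check compares the text with the outputs and then asks what the planned tables can and cannot show.

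**1. Examination: stated outcome against planned output.**
- In-clinic vital signs and weight: SAP 11.1.4 gives change from both the first-implant and most-recent-implant baselines, in the listing.
- Continuous ECG parameters: SAP 11.1.5 summarises change from both baselines.
- Body-system findings: SAP 11.1.6 summarises abnormal status only.

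The mismatch is confined to the third item.

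**2. Examination: what prevalence leaves open.** Let *n* subjects be examined at both times, with *a* abnormal at baseline and *b* abnormal at one later visit. The number abnormal at both lies between max(0, *a* + *b* − *n*) and min(*a*, *b*). New findings equal *b* minus that overlap, so they lie between max(0, *b* − *a*) and min(*b*, *n* − *a*).

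Group sizes come from the documents: 20 colorectal subjects (SAP 3.2), or 74 − 40 = 34 (Protocol Appendix 3, item 9). The prevalences below are assumed, because the documents give none.

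| *n* | *a* = *b* | Lower limit | Upper limit |
|---|---|---|---|
| 20 | 2 (10%) | max(0, 0) = 0 | min(2, 18) = 2 |
| 20 | 10 (50%) | max(0, 0) = 0 | min(10, 10) = 10 |
| 34 | 17 (50%) | max(0, 0) = 0 | min(17, 17) = 17 |

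These are limits, not estimates. The per-subject listing resolves them; the table does not.

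**3. Laboratory: which grade rises a normal/abnormal shift shows.** Taking Grade 0 as normal and grades 0 to 4 as possible, there are 4 + 3 + 2 + 1 = 10 worsening transitions.
- From a normal baseline: 0→1, 0→2, 0→3, 0→4. These 4 count as shifts.
- From an abnormal baseline: 1→2, 1→3, 1→4, 2→3, 2→4, 3→4. These 6 do not.

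Of those 6, 5 end at Grade 3 or 4 and so fall in Listing 16.2.8.4. The exception is 1→2, which reaches neither that listing nor the TEAE tables unless it is reported as an adverse event.

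**4. Laboratory: can the by-grade tables recover the count?** Not in general. Take 15 subjects, five each at Grades 1, 2 and 3 at baseline.
- Scenario A: nobody changes.
- Scenario B: five go 1→2, five go 2→3 and five go 3→1.

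Both scenarios end with five subjects at each grade, and both have 0 normal/abnormal shifts. The number who worsened is 0 in A and 5 + 5 = 10 in B. The example is constructed: it needs improvements that exactly offset the worsening.

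**The case against.** The strongest case is that worsening is already visible by several routes, which leaves a preference about table layout.

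**Laboratory.** A reader might infer that the SAP plans nothing that would reveal deterioration from an abnormal baseline. The documents do not support that.
- The reference to toxicity grades in the shift-table sentence leaves a grade-by-grade layout possible, and the table titles do not settle it.
- Tables 14.3.4.1.1 and 14.3.4.2.1 present observed values and changes for chemistry and hematology; SAP 11.1.3 plans these for select parameters, from both baselines.
- Tables 14.3.4.1.4 and 14.3.4.2.4 are the by-grade tables, and Listings 16.2.8.2.1.1 and 16.2.8.2.2.1 give toxicity grades.
- Listing 16.2.8.4 holds Grade 3 or higher and AE-reported values.
- Protocol 6.1 makes clinically significant laboratory values adverse events, and SAP 11.1.2 counts events that worsen as TEAEs.

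All of this stands. What remains is that none of these outputs is described as counting subjects whose grade rose from their own abnormal baseline, and that the wording of the shift tables is unclear.

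Inclusion item 6 is also weak evidence for the laboratory point, since it concerns residual toxic effects and is not a laboratory criterion. It bears more directly on examination findings.

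**Examination.** A reader might infer that the whole outcome in SAP 3.3.2 goes unanalysed as change. It does not, as step 1 of the working shows. SAP 6.1 generally orders tables by study day, so if Table 14.3.5.1 follows that rule, change in group prevalence can be read. The listing shows each subject's status, and with groups this small it can be read directly. These points limit the consequence, but the table still omits the number of subjects with a new finding.

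**Consequence.** SAP 6.2 makes all analyses exploratory, and the study stopping rule (Protocol 6.6) counts Grade 5 events. That stands, and it keeps the point at the level of an optional improvement.

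**Conclusion.** The point holds as a minor one. For body-system findings, SAP 11.1.6 and Table 14.3.5.1 do not deliver the change-from-baseline outcome that SAP 3.3.2 states, because long-standing and new findings are counted alike. This part rests on the text alone.

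The laboratory part is secondary and depends on reading the shift tables as normal/abnormal only. On that reading a grade rise from an abnormal baseline is not counted per subject. The part that escapes both the Grade 3 or higher listing and the TEAE tables is mainly a Grade 1 to 2 rise not reported as an adverse event, and the graded listings may still show it.

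No number of affected subjects can be given, since the documents contain no baseline abnormality rates. The ranges in the working rest on assumed, equal prevalences and on all subjects being examined at both times. The documents do not support saying that a safety signal would be missed, or that any trial decision would change.

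**What to change.** **Main change (SAP 11.1.6, Table 14.3.5.1).** Beside the planned prevalence, add for each body system the number and percent of subjects who were normal before the first implant and abnormal at any later scheduled visit. Use as denominator the subjects examined both before the first implant and later.

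**Secondary change (SAP 11.1.3, Tables 14.3.4.1.3 and 14.3.4.2.3).** For CTCAE-graded parameters, cross-tabulate the grade before the first implant by the worst post-baseline grade. Give the number and percent worsening by 1 or more grades and by 2 or more grades. Keep the planned shifts by visit and from the most recent implant, and keep range-flag shifts for parameters that have no CTCAE grade.

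**Cost.** SAP wording, table shells and the associated programming. Examination status is already collected and toxicity grades are already derived. No new data, visits or subjects are needed.

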11.1.4 Vital signs and weight

Vital signs (blood pressure, respiration rate, heart rate, and temperature) and weight will be obtained at each study visit. In addition, at-home blood pressure, heart rate, and temperature recordings will be logged by subjects or their caregivers twice daily at 8 A.M. and 8 P.M. for the first month after implantation, then once a day for the following two months. The investigators may modify this schedule, depending on clinical circumstances. Both in-clinic and at-home data will be recorded in the CRF. In-clinic and at-home vital signs will be listed separately. Listings will include the study day, date and observed values. In-clinic data will include the change from baseline in relationship to both first and most recent implant. At-home data will be considered unscheduled data, and will be listed but will not be summarized or analyzed.

11.1.5 12-Lead electrocardiogram (ECG)

Data from standard 12-lead ECGs will be recorded in the CRF. The following parameters will be collected: rhythm (normal / abnormal), heart rate, and PR, QRS, QT and QTcB intervals. The listing will include study day, date, observed values, and, for continuous parameters, change from baseline in relationship to both first and most recent implant. At each time point, observed values and changes from baseline in relationship to both first and most recent implant will be summarized for continuous parameters; nominal parameters will be categorized and summarized as frequencies and percentages of subjects at each time point.

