If deemed medically and surgically safe by the operating surgeon, one or more biopsies of tumor mass will be taken during this procedure. Fresh frozen tissue and fixative-treated tissue will be sent to the laboratory for immunohistochemical and gene array analysis to determine baseline tumor histopathology and gene expression patterns.

5.1.5 Home Care:

Post-surgical home care requirements are expected to be minimal. Medical and wound care regimens will be carried out as individually prescribed by the investigators and appropriate physicians directly involved in the subject's care. The subject will complete a daily log of activity (ADL) and a general symptom checklist (defined subjectively), but with special emphasis on appetite, abdominal symptoms such as pain or cramping, bowel movements, urination (frequency,

dysuria), and pain medication requirements. Both the subject and her/his family members will be trained in the simple vital sign measurements and the filling in of the activity log/assessment and symptom checklist. Vital signs will be measured twice daily at 8am and 8pm for the first month after implantation, then once a day for the next two months. The investigators may modify this schedule, if the clinical circumstances demand such modification. Subject and family training will take place prior to macrobead implantation, with a review prior to discharge after implantation.

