6.7 Potential Risks

Animal and human subjects studies to date have defined the parameters of the safety of the RENCA cancer macrobeads. In summary, the RENCA macrobeads have been well tolerated in murine tumor models, in cats and dogs with naturally occurring tumors of various types, where the RENCA macrobeads have now been implanted for periods of up to four years. Furthermore, in 13 humans with end-stage cancer implanted with the macrobeads (up to 17 months), no serious adverse events have been recorded which can be attributed to the macrobeads. Typically, the animals undergoing implantation have exhibited improved appetite, weight gain, and increased activity levels (the latter have been remarkable in at least one half of the animals treated). Adverse reactions observed to date have been 1) mild-to-moderate intraperitoneal chronic inflammatory reaction evident after 3 months in cats and dogs, but not mice; and 2) entrapment of some macrobeads in the feline and canine omentum. In the humans the reactions have been mild as well. Some subjects have experienced mild, intermittent fevers after implantation (generally resolved by four to six weeks after implant).

A mild-to-moderate inflammatory reaction to the intraperitoneal placement of the macrobeads has been noted in humans and veterinary patients, but not mice. In the cats and dogs, where the RENCA macrobeads have been implanted for periods of up to four years, this reaction becomes apparent beyond three months. It consists of a minimal to moderate increase in inflammatory markers, with no disruption of normal physiological functions, such as those of intestinal peristalsis or biliary or pancreatic drainage/secretion. Neither has it interfered with subsequent re-implantations of the RENCA macrobeads when indicated. In humans, implantation has led to an increase in inflammatory markers, with intermittent, self-limiting, low grade fevers in some cases. However, as observed in animals, the reactions were mild and not accompanied by clinical limitations.

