6.2 Data Analysis

- All analyses will be done using SAS® version 9.1.3 or higher.
- All analyses will be exploratory. No confirmatory statistical testing will be done.
- Categorical variables will be summarized as frequencies and percentages in each category. In general, continuous variables will be summarized by numbers of patients, means, standard deviations, medians and ranges. The number of decimal places for minimums and maximums will be the same as the original data. The number of decimal places for means, medians and interquartile ranges will be the same as the original data plus one. The number of decimal places for measures of variance will be the same as the original data plus two.
- Laboratory data with qualifiers (e.g., "<") will be listed with but summarized without the qualifier.
- All p-values will be presented as illustrated below:

p-value	Presentation
≥ 0.01	2 decimal places
< 0.01 but ≥ 0.001	3 decimal places
< 0.001 but ≥ 0.0001	4 decimal places
< 0.0001	< 0.0001

- All analyses will be exploratory and, as such, there will be no significance level adjustments to control type I error.
- All statistical tests will be two-sided.
- Unscheduled data will not be summarized or analyzed (but will be listed, as noted above).

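### SAP 11.1.4 says scheduled home temperatures will not be summarized, but the SAP table list plans a diary vital-signs table; if the text is followed, unreported mild fever, recurrence and duration go unsummarized

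*SAP*

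**What the plan says.** Protocol 6.7 describes the reaction twice. First: "Some subjects have experienced mild, intermittent fevers after implantation (generally resolved by four to six weeks after implant"). It then reports "intermittent, self-limiting, low grade fevers in some cases", in humans, alongside raised inflammatory markers.

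Protocol 5.1.5 (Home Care) trains subjects and families to take vital signs, which are to be "measured twice daily at 8am and 8pm for the first month after implantation, then once a day for the next two months". Investigators may modify that schedule.

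SAP 11.1.4 confirms that "at-home blood pressure, heart rate, and temperature recordings will be logged by subjects or their caregivers twice daily" in the first month, and that these values go into the CRF. It closes with "At-home data will be considered unscheduled data, and will be listed but will not be summarized or analyzed". SAP 6.2 applies the same treatment generally: "Unscheduled data will not be summarized or analyzed (but will be listed, as noted above").

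SAP 16.2 lists Table 14.3.6.1 for vital signs and, separately, Table 14.3.6.2, "Vital signs from diary". SAP 16.1 keeps a listing of the home-care log (16.2.9.4.2). No SAP text specifies the content of Table 14.3.6.2.

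**The concern.** An intermittent fever is poorly captured by occasional clinic readings. The home log is the only dense temperature record in the trial, and it covers the weeks in which the protocol says these fevers occur. Calling it unscheduled does not fit the SAP's own use of that word: SAP 6.4.2 and 6.4.4 apply it to observations and visits outside the visit windows, whereas the home readings have times fixed by the protocol.

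A programmer cannot obey both SAP 11.1.4 and SAP 16.2. If the text prevails, how often home-measured fever occurs, how long it lasts and whether it changes with successive implants will not be summarized. Those questions matter here. Safety and tolerability are the secondary objective (SAP 3.1), the trial is meant to supply estimates for planning later trials (SAP 3.2), and Protocol 6.5.1 expects toxicity to follow the number of implantations more than the number of beads per implantation.

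**Working it through.** The plan gives no figure on this point, so there is none to reproduce. The check counts readings and then follows each rule.

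**Clinic temperatures after an implant, to week six (day 42).** Protocol 5.1.6 to 5.1.8 set visits at Day 14 ± 3, Day 30 ± 5 and Day 60 ± 5. The Day 60 visit cannot fall before day 55 (day 53 under the SAP window). That leaves two visits by day 42. Vital signs on the implant day would make three if Day 0 is counted.

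**Home readings scheduled, taking a month as 30 days.**
- To day 28: 28 × 2 = 56
- To day 42: 30 × 2 + 12 × 1 = 72
- To day 90: 30 × 2 + 60 × 1 = 120

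These are maxima. They assume that the schedule is not modified and that every reading is taken.

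**Would deleting the sentence in SAP 11.1.4 be enough?** No. The windows in SAP 6.4.4 are days 7–21, 23–37, 53–67 and 83–97. Up to day 42, the days outside any window are 1–6, 22 and 38–42.
- Home readings outside a window: 6 × 2 + 1 × 2 + 5 × 1 = 19 of 72. SAP 6.4.2 would label these unscheduled.
- Home readings inside a window: 15 × 2 (days 7–21) + 8 × 2 (days 23–30) + 7 × 1 (days 31–37) = 53. SAP 6.4.3 keeps the last valid observation per window, so these reduce to two values.

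By default, then, Table 14.3.6.2 would carry two values per subject for the first six weeks and nothing from the first six days.

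**The adverse event route.**
- Protocol 6.1 defines an adverse event broadly enough to include fever. SAP 11.1.2 tabulates treatment-emergent events by preferred term and by implantation number.
- SAP 11.1.6 has a rule sending qualifying physical examination changes to the adverse event form. SAP 11.1.4 has no such rule for vital signs, at home or in clinic.
- SAP 11.1.2 counts a repeated event once per subject, and gives onset, resolution and duration in listings only.

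Reported fever is therefore summarized as incidence. Recurrence, duration and unreported mild fever are not.

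**Illustration only.** Let *f* be the share of readings that are febrile in an affected subject. The documents give no value, so *f* is assumed, and readings are treated as independent. P(at least one febrile reading) = 1 − (1 − *f*)ⁿ.

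| *f* | 2 clinic readings | 3, with Day 0 | 72 home readings |
|---|---|---|---|
| 5% | 10% | 14% | 97.5% |
| 10% | 19% | 27% | 99.95% |
| 20% | 36% | 49% | >99.9% |
| 30% | 51% | 66% | >99.9% |

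Fevers that cluster in time, or missed home readings, would lower the last column.

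**The case against.** The strongest reply is that fever is not lost. It qualifies as an adverse event. Events are volunteered, observed and elicited from consent to 120 days after the last implant (SAP 11.1.2), and Protocol 5.3 adds telephone contact between visits. Incidence is tabulated by implantation number, and every home value remains in a listing. The protocol calls the reactions mild and without clinical limitation, all analyses are exploratory, and the primary outcome is untouched. Dropping Table 14.3.6.2 from the list would also end the contradiction.

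Most of this stands, and it rules out three stronger readings that a reader might infer:
- That the SAP definitively excludes home temperatures from summary. The table list says otherwise, so the supported finding is a conflict.
- That post-implant fever would be known only from two clinic readings. This holds for summarized temperature measurements, not for reported fever.
- That about 97% of the temperature data are discarded (120 of 120 + 4 clinic readings). This counts readings, not information. It also assumes full compliance and that the text overrides the table list.

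The reply does not cover fevers that were measured but not reported, nor recurrence and duration. Dropping the table would remove the inconsistency but leave that gap.

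**Conclusion.** The SAP contradicts itself on whether home vital signs are summarized, and that finding needs no assumption. If the text rule is followed, summarized temperature measurements between the implant day and week six come from two visits per implant, against up to about 72 scheduled home readings. Reported fever still reaches the adverse event tables; unreported mild fever, recurrence and duration reach listings at most.

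The count of 72 assumes a 30-day month and an unmodified, fully completed schedule. Applying it to every implant assumes that the log is repeated each time. Protocol 5.1.5 follows the first implant, and the later implant sections mention home care without restating the schedule. The detection probabilities show direction only.

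This is a correction worth making to the safety reporting. It does not threaten the efficacy analysis.

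**What to change.** In the SAP:

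1. Delete the last sentence of 11.1.4. The separate listing of home values is already provided for earlier in that section.
2. Keep Table 14.3.6.2 and exempt diary data from the visit-window and last-observation rules in 6.4.2 to 6.4.4.
3. Specify the table by cancer type and implantation number, among subjects with at least one home reading:
   - maximum home temperature
   - number and percentage of subjects with any reading at or above a prespecified reporting threshold
   - number of days at or above it
   - day of the last such reading after the implant
   - percentage of expected readings completed
4. State the threshold in advance. A value of 38.0 °C would serve as an illustration; it does not come from the documents. Because the protocol describes low-grade fever, the maximum should be shown whatever threshold is chosen.
5. State whether the log is kept after every implant, so that the expected number of readings is defined.

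The cost is SAP wording and the programming of one table already on the list, from data already entered in the CRF. The downside is that self-measured data will be less complete, which the completion rate discloses.
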